4.10 The Number of Participants

- 12-14 participants will be recruited for this phase of the study. No formal power calculation has been performed as this is a feasibility study.

Post-trial focus groups or interviews:

All participants in the four-week trial of BR will be asked to participate in one of the post-trial focus groups or an interview. With a trial withdrawal rate of 10%, this will mean at least 10 participants complete the trial and are eligible for the focus groups. A minimum number of participants for each focus groups is 3 and we estimate that 3-4 focus groups will be needed.

5.0 Phase 2: Biologic priming study

5.1 Study Aims

- To assess the feasibility of running a remote BR course before patients commence a biologic treatment for their severe asthma.
- To assess the acceptability of BR, testing a modified intervention having learned lessons from this feasibility study, testing the performance of outcome measures to inform a potential randomised controlled trial of the intervention.

5.2 Primary objectives

- To identify patients due to commence a biologic treatment for their severe asthma in normal care and offer them the opportunity to undertake the BR programme.
- To run a BR course with these patients and assess process outcomes, quantitative and qualitative measures of the impact of the course.
- To develop an information booklet on the principals of BR for patients with Severe Asthma who are starting or have started a biologic.

5.3 Inclusion criteria

- Diagnosed with severe asthma as per ERS/ATS definition.
 - Requiring high dose inhaled corticosteroids (NICE definition of high dose ICS, Appendix 2).
- Patients with severe asthma who have been approved for biologic treatment according to national guidance and have been assessed by a multi-disciplinary team will be offered the intervention pending starting their biologic treatment.
- Patients with eight or more non-respiratory symptoms per week as measured by the GSQ.

5.4 Exclusion criteria

- Unable or unwilling to take part.
- Participated in phase 1 of the study
- In the opinion of the patient's treating physician, the patient has another condition which is significantly impairs their ability to take part in BR.

5.5 Recruitment and consent

Before commencing a biologic treatment for severe asthma in normal clinical care, patients are reviewed by a Multi-Disciplinary Team (MDT) responsible for their care. The PI at the participating hospital will identify patients eligible to take part in this study at this time. Recruitment of eligible patients will then proceed as outlined in phase one. Participants will be sent a Patient Invitation Letter (Appendix 14) and Patient Information Leaflet (Appendix 15) that describe phase two of the study.

5.6 Data collection Method

Questionnaire collection time points are the same as for phase one:

- The first and last week.

Demographic and clinical information will be the same as for phase one.

The outcome measures will be the same as for phase one.

The Global Rating of Change Questionnaire (GRCQ) (Appendix 16)

In this phase of the study the GRCQ will be used by participants to indicate how much better they feel since commencing a **BR and a biologic treatment**. The 11-point scale ranges from -5 (a great deal worse) to 5 (A great deal better) [17].

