FOR QUALITATIVE DATA	19
4.10 THE NUMBER OF PARTICIPANTS	19
5.0 PHASE 2: BIOLOGIC PRIMING STUDY	19
5.1 STUDY AIMS	19
5.2 PRIMARY OBJECTIVES	20
5.3 INCLUSION CRITERIA	20

5.4	EXCLUSION CRITERIA	20
5.5	RECRUITMENT AND CONSENT	21
5.6	DATA COLLECTION METHOD	21
5.7	DESCRIPTION OF STATISTICAL METHODS	21
5.8	THE NUMBER OF PARTICIPANTS	21
5.9	THE LEVEL OF STATISTICAL SIGNIFICANCE	22
5.10	WITHDRAWAL CRITERIA FOR BOTH PHASE ONE AND PHASE TWO	22
6.0	ETHICAL AND REGULATORY CONSIDERATIONS / ROLE OF SPONSOR	22
6.1	ASSESSMENT AND MANAGEMENT OF RISK	22
6.2	RESEARCH ETHICS COMMITTEE (REC) AND OTHER REGULATORY REVIEW & REPORTS	22
6.3	REGULATORY REVIEW & COMPLIANCE	23
6.4	PROTOCOL COMPLIANCE	23
6.5	DATA PROTECTION AND PATIENT CONFIDENTIALITY	24
6.6	INDEMNITY	24
6.7	ACCESS TO THE FINAL STUDY DATASET	24
7.0	REFERENCES	26
APPENDIX 1: GANTT CHART		27
APPENDIX 2: NICE DEFINITION OF HIGH DOSE INHALED CORTICOSTEROIDS		28

Glossary of Abbreviations

AE	Adverse event
AR	Adverse reaction
CI	Chief Investigator
CRF	Case Report Form
CT	Clinical Trials
DMC	Data Monitoring Committee
GCP	Good Clinical Practice
GP	General Practitioner
ICF	Informed Consent Form
ICH	International Conference of Harmonisation
NHS	National Health Service
NRES	National Research Ethics Service
PI	Principal Investigator
PIS	Participant/ Patient Information Sheet
R&D	NHS Trust R&D Department
REC	Research Ethics Committee
SAE	Serious Adverse Event
SAR	Serious Adverse Reaction
SmPC/SPC	Summary of Products Characteristics
SOP	Standard Operating Procedure
TMF	Trial Master File
TSG	Trials Steering Group
SAQ	Severe Asthma Questionnaire
ACQ	Asthma Control Test
GINA	Global Initiative for Asthma
GRCQ	Global Rating of Change Questionnaire

Keywords

Severe Asthma

Biologic treatment

Body Reprogramming

Study Summary

Title	Body Reprogramming as an adjunct to biologic administration in patients with symptomatic Severe Asthma: a feasibility study
Design	A feasibility study of Body Reprogramming (BR) in 2 patient groups one as an addition to normal treatment and one provided before starting a biologic treatment
Aims	
 • To assess the feasibility and acceptability of BR to people with severe asthma, • Using patient and other feedback to adapt and optimise the intervention for people with severe asthma.

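### The Phase 2 Global Rating of Change question asks about change since starting BR and a biologic, but its only post-course time point is the last week of a course meant to run before the biologic starts

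*Combined protocol and SAP*

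**What the plan says.** Section 5.6 describes the Phase 2 GRCQ as used by "participants to indicate how much better they feel since commencing a BR and a biologic treatment", on an 11-point scale from -5 to 5. On timing it says "Questionnaire collection time points are the same as for phase one" and then lists "The first and last week". Section 4.7 shows that in Phase 1 these are the first and last weeks of the BR course. Section 4.8 puts the GRCQ under its post-course heading and words the Phase 1 version as change since starting BR, with no mention of a biologic.

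Three places put the Phase 2 course ahead of the biologic. The Study Summary describes two patient groups, "one provided before starting a biologic treatment". Section 5.1 aims to assess a course run "before patients commence a biologic treatment for their severe asthma". Section 5.3 says that approved patients "will be offered the intervention pending starting their biologic treatment".

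Section 5.1 also gives Phase 2 the aim of "testing the performance of outcome measures to inform a potential randomised controlled trial of the intervention". Section 5.7 adds a look for trends between the two phases.

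**The concern.** A global rating of change means something only against its reference point: the respondent must know since when, and since what, change is being judged. Here the wording names two starting events, and on the plan's own sequence only one has happened when the form is completed. Participants may ignore the biologic, answer about BR, or be confused, and the data will not show which.

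This bears on a stated aim, because Phase 2 is meant to show how the outcome measures perform before a possible randomised trial. A GRCQ with a reference point that does not fit its time point cannot be judged fairly. The two phases would also have been asked different questions, so a difference in GRCQ scores between them could come from the wording alone. The full statistical analysis plan, which section 4.9 promises before final data extraction, cannot repair this, since it cannot reword a question already answered.

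**Working it through.** The plan states no figure for this point, so the check is one of order, followed by a count.

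**Order of events**

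| Element | What the plan gives | Where |
|---|---|---|
| GRCQ reference point, Phase 1 | start of BR | 4.8 |
| GRCQ reference point, Phase 2 | start of BR and of a biologic | 5.6 |
| Collection points, both phases | first and last course week | 4.7, 5.6 |
| Place of the GRCQ | post-course | 4.8 |
| Order of course and biologic | course first | Study Summary, 5.1, 5.3 |

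1. Of the two collection points, a post-course form can use only the later one, the last week.
2. The course is to run before the biologic, so its last week precedes the biologic start.
3. Planned biologic exposure at the GRCQ is therefore zero. This does not depend on course length: if the course is adapted after Phase 1, the last week of a course run before the biologic still precedes it.

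**Ratings affected**

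- Section 5.8 recruits 12-14 participants, each giving one post-course rating: 1 × 12 = 12 to 1 × 14 = 14, an upper limit.
- If the 10% withdrawal in section 4.10 for Phase 1 also held in Phase 2 (an assumption), 12 × 0.9 = 10.8 and 14 × 0.9 = 12.6, or 10-12 whole completers. Returned ratings could be fewer, because no GRCQ return rate is given.

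**What is not affected**

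The GRCQ has no baseline value, so it does not enter the pre/post differences or the analysis of covariance in section 4.9. Uptake, attendance, completion and the Friends and Family Test do not depend on its wording.

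**Late returns**

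Section 4.7 re-sends an unreturned pack after two weeks and telephones after two more. If the four-week length is kept, a late pack could come back at about week 4 + 2 + 2 = 8 or later. Some could then be completed after a biologic start, in numbers the documents do not give. This would be unplanned and would vary between participants; it is not a defined assessment after the biologic. Section 5.6 says "Demographic and clinical information will be the same as for phase one", and section 4.7 collects that information at baseline, so a later biologic start date is not a listed variable.

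**The case against.** The strongest reply is that the sequence is less fixed than it looks. Section 5.3 only offers the course while the biologic is pending, section 3 speaks of patients expected to start one, and biologics are given in normal care. Nothing says the biologic waits for the last course week. Some overlap is possible, and the wording may anticipate it. This stands to the extent that the count of 12-14 is conditional on the stated order. It does not rescue the wording: with overlap, some participants would be rating BR alone and others BR plus a biologic under the same question.

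A second reply is that the Gantt chart and the Appendix 16 form are not visible, and section 4.9 mentions listed time points after the trial. A later time point or different form wording cannot be ruled out. Even so, section 5.6 lists two time points and no other, and would need correcting to agree.

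A third is that section 5.7 looks only for trends, and that the phases already differ in population and in BR content adapted after Phase 1. That is fair. Matching the wording removes one avoidable difference; it does not make the phases like for like.

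A reader might go further and infer that Phase 2 fails because nothing measures response to the biologic after BR. The documents do not support this. Section 1.2 expresses a hope about that response, but no objective in 5.1 or 5.2 requires an outcome after the biologic starts. Nor can it be said that the plan omits completion dates, since the questionnaire forms are in appendices not shown.

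**Conclusion.** The inconsistency is real and lies within section 5.6 and between it and section 5.1, section 5.3 and the Study Summary. If the course precedes the biologic as stated, up to 12-14 GRCQ ratings would be given under a question about a treatment not yet begun, and the GRCQ would not be comparable between phases.

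The consequence is confined mainly to this one instrument, and no effect size is claimed. It would be tempting to conclude that the Phase 2 ratings then measure BR alone. In an uncontrolled study that does not follow: they would exclude the biologic, but could still carry natural variation, other treatment changes or expectation. The conclusion rests on the visible text and on the stated order of course and biologic. It is worth correcting because testing outcome measures is an aim of Phase 2 and the correction is nearly free.

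**What to change.** - In section 5.6 and the Appendix 16 form, reconcile wording and time point by using the Phase 1 reference point, change since starting BR, at the last week.
- In section 5.7, state that the GRCQ is compared between phases only where the wording is the same.

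The cost is a small amendment, with the HRA and local R&D review that section 6.2 requires if the protocol is already approved. The loss is that no combined BR-and-biologic rating is obtained. If the sponsor wants one, it belongs at a stated time after the biologic start. That is an optional addition, costing one further mailing per participant (at most 12-14) and tracking of start dates within the 15-month study.

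Also optional: record one date for the last-week pack and take the biologic start date from clinic records, so that any pack completed after a biologic start can be flagged. At two dates per participant that is 2 × 12 = 24 to 2 × 14 = 28 entries. Nothing here changes when any treatment is given.

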5.7 Description of Statistical Methods

The statistical methods will be the same as that for phase one. The researchers will examine whether there is any trends indicating differences in outcome between phase one and phase two

5.8 The Number of Participants

- 12-14 participants will be recruited for this phase of the study. No formal power calculation has been performed as this is a feasibility study. Two groups of BR will be run.

5.9 The Level of Statistical Significance

Not applicable

5.10 Withdrawal criteria for both phase one and phase two

Whilst participating in the study, a patient's health or diagnosis may change. If this occurs during the study, the participant eligibility for the study they are in will be re-assessed by the clinician responsible for their care. If the participant no longer meets the eligibility criteria, their data will be removed from the database. The patient will be thanked for their time and told not to expect to be asked to participate further.

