Outcome Measures	
 • Number and percentage of participants taking part and completing the course including those completing the following questionnaires 
 ○ Severe Asthma Questionnaire (SAQ) ○ General Symptom Questionnaire (GSQ) or GSQ-Asthma (GSA-A) ○ Positive and Negative Affect Schedule (PANAS) ○ Asthma Control Questionnaire (ACQ) ○ Global Rating of Change questionnaire (GCRQ) • Attendance to Body Reprogramming Zoom calls • Feedback received using the Friends and Family Test (FFT) 
Qualitative data from the focus groups or interviews analysed using thematic analysis concerning participants' experiences of Body Reprogramming.

Population	Patients with symptomatic severe asthma attending the regional severe asthma clinic in RD&E Hospital Devon.
Eligibility	
Phase 1
 
Patient has severe asthma as per ERS/ATS definition and is receiving high dose inhaled corticosteroids as defined by NICE (Appendix 2)
 
AND
 
Eight or more non-respiratory symptoms per week recorded on the GSQ
 
Phase 2
 
Patients with severe asthma who have been approved to commence a biologic treatment for their severe asthma

Duration	15 months
Timelines	See Gantt Chart (Appendix 1)

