4.2 Primary objectives

Four-week trial of BR

- To assess patients' willingness to attend BR and engage with the intervention as measured by course attendance and by their written feedback.
- To record the user experience when participating in the trial.
- To assess patient's willingness to complete a series of questionnaires
- To get patient feedback on the appropriateness of the questionnaires for assessing improvement in larger future studies

Post-trial focus groups or interviews

- To gain qualitative feedback on patients experience of BR following their participation in the four-week trial.
- To assess the acceptability of BR for people with severe asthma.
- To understand the barriers to attending BR by speaking those who did not attend the course.

- Using all the data from participants we will adapt the BR programme before commencing phase two.

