4.4 Exclusion criteria

- Unable or unwilling to partake.
- In the opinion of the patient's treating physician, the patient has another condition which is significantly impairs their ability to take part in the BR.
- No access to the internet or appropriate IT equipment

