4.7 Data collection time points

Participants will be asked to complete a series of questionnaires (see section 4.8) when they attend the Body Reprogramming course during the first and last week. These will be posted to the participant's home address by a research nurse, completed, and returned to the patients' clinic using a FREEPOST envelope.

At the end of the course, participants will be asked to complete a course feedback form.

If participants have not returned the questionnaire within two weeks the questionnaire pack will be sent out again. If a further two weeks pass without the return of questionnaires a researcher will contact participant by phone and ask if they need assistance.

Patients will be asked to text or email the course co-ordinator if they are unable to attend a course date for any reason. Experience shows that health and other problems can prevent patients from attending, so attendance monitoring requires this form of data.

Demographic data

The following demographic and clinical information will be collected from the participants' clinical records at baseline by a researcher:

Patient demographics:

- Age
- Sex
- Ethnicity
- Smoking status

Clinical data

Most recent spirometry (in the last 6 months),

Major co-morbidities (respiratory and non-respiratory as identified by the patient's clinician)

- Current Drug treatment
- Asthma exacerbations requiring systemic steroids in the last 12 months,
- Cumulative steroid burden in the last 12 months,
- Healthcare utilisation: hospital admissions / Emergency Department attendances in the last 12 months.

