4.9 Description of Data analyses

For quantitative data

This is a feasibility study and so not powered for statistical testing. This section describes the data to be collected which will inform the design of future studies.

- The number and percentage of participants that are invited, attended and completed the BR course will be reported.
- All outcome measures will be summarised using means and standard deviations or median (range, IQR) for continuous outcomes (as appropriate), and frequencies and proportions for categorical outcomes.
- The mean difference in all recorded scores (pre and post-trial at listed time points post-trial) will be estimated and in addition using an analysis of covariance of the baseline value of the score as well as disease severity as a covariate in the model.
- The number and percentage with complete data will be reported. The missing value guidance provided for questionnaires will be used. If no guidance is provided values

will be imputed for an individual if 20% or fewer items are missing. If greater than 20% of items are missing in the questionnaire then the questionnaire score will be treated as missing and excluded from the analysis.

- The number of adverse events (AE) and serious adverse events (SAE) will be tabulated also by the number of patients reporting an event. No dictionary for coding adverse events will be used. Events will be recoded using terms of the clinical investigators choosing.
- A full statistical analysis plan will be drawn up and agreed by the CI and study team prior to the final data extraction.

For qualitative data

Once transcribed, the audio recordings from the focus groups or one to one interviews will be analysed for recurring themes. The information gained from this phase will be used to make changes to practical aspects of the BR course, e.g. length of meetings or number of weeks, as well as adapt the narrative of the course for patients with severe asthma if required.

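### Section 5.10 deletes the data of participants who lose eligibility after a change in health, with no exemption for completion, attrition or adverse event data

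*Combined protocol and SAP*

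**What the plan says.** Section 5.10 applies to both phases. A change in health or diagnosis prompts the responsible clinician to re-assess eligibility. The consequence is unqualified: "If the participant no longer meets the eligibility criteria, their data will be removed from the database". The person is then thanked and "told not to expect to be asked to participate further". The term database is not defined.

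One route to losing eligibility is written into the exclusion criteria. Section 4.4 excludes a patient if, in the treating physician's opinion, "the patient has another condition which is significantly impairs their ability to take part in the BR"; section 5.4 repeats this for Phase 2.

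The results exposed to the rule are these:

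- The Study Summary lists as an outcome "Number and percentage of participants taking part and completing the course".
- Section 4.9 says: "The number and percentage of participants that are invited, attended and completed the BR course will be reported". It also calls for AEs and SAEs to be tabulated by event and by patient.
- Section 6.7 names uptake, completion and attrition proportions as part of the final dataset.

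Two other places bear on the point. Section 4.7 explains why absences are to be notified: "Experience shows that health and other problems can prevent patients from attending, so attendance monitoring requires this form of data". Section 4.2 sets as a Phase 1 objective "To understand the barriers to attending BR by speaking those who did not attend the course".

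**The concern.** The trigger for deletion is related to the outcomes. A participant who falls ill and cannot continue is a natural candidate for losing eligibility, a likely non-completer, and possibly a patient with an AE or SAE. Deleting that person's data removes a case that the completion, attrition and safety summaries exist to show.

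It also works against the plan's own reasoning: section 4.7 treats health-related absence as needed information, and section 4.2 wants to learn what stops people attending. The instruction that such participants should not expect further contact makes it unclear whether they would be interviewed. Section 4.10 does not settle this, because it first says all participants will be asked and then ties focus-group eligibility to completing the trial.

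At stake is the description that a later trial would be designed on. Completion would tend to look better than it was, attrition lower, and the AE/SAE counts could only stay the same or fall.

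**Working it through.** **Inputs.** Recruitment is 12 to 14 per phase (sections 4.10 and 5.8). Section 4.10 assumes 10% withdrawal and at least 10 completers. The documents give no rate for loss of eligibility during the study, so the numbers removed below are assumptions.

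**The plan's own figure.** 12 × 0.9 = 10.8, which is 10 whole participants; 14 × 0.9 = 12.6, which is 12. The lower end reproduces the stated minimum of 10. The 10% covers withdrawal for any reason (1.2 of 12, 1.4 of 14) and is not used here as the rate of lost eligibility.

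**Direction.** Let c of n enrolled participants complete, and let m be removed, k of them completers. Reported completion moves from c/n to (c − k)/(n − m). It rises when k/m < c/n, that is, when the removed complete less often than the whole group. It falls when a completer is removed.

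**Completion among enrolled participants, exact (Clopper-Pearson) 95% intervals**

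| Assumed case | All enrolled kept | After removal | Shift (points) |
|---|---|---|---|
| n = 12, one non-completer removed | 11/12 = 91.7% (62 to 99.8) | 11/11 = 100% (72 to 100) | +8.3 |
| n = 14, one non-completer removed | 13/14 = 92.9% (66 to 99.8) | 13/13 = 100% (75 to 100) | +7.1 |
| n = 12, one completer removed | 11/12 = 91.7% | 10/11 = 90.9% (59 to 99.8) | −0.8 |
| n = 14, one completer removed | 13/14 = 92.9% | 12/13 = 92.3% (64 to 99.8) | −0.5 |
| n = 12, two non-completers, one removed | 10/12 = 83.3% (52 to 98) | 10/11 = 90.9% | +7.6 |
| n = 12, two non-completers, both removed | 10/12 = 83.3% | 10/10 = 100% (69 to 100) | +16.7 |

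In the last row attrition goes from 2/12 = 16.7% to 0/10 = 0%. That row is an upper illustration: it takes the plan's minimum of 10 completers and supposes that both others lost eligibility.

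**Safety.** If the only SAE is in the removed participant, 1/12 = 8.3% (0.2 to 38) becomes 0/11 = 0% (0 to 28). If the removed participant had no SAE, the count stays at 1 and the proportion moves from 8.3% to 1/11 = 9.1% (0.2 to 41).

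**How likely is at least one case?** The chance per phase is 1 − (1 − p)^n, with p assumed:

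- p = 0: 0%.
- p = 2%: 1 − 0.98^12 = 22%; 1 − 0.98^14 = 25%.
- p = 5%: 1 − 0.95^12 = 46%; 1 − 0.95^14 = 51%.

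**Does any other text undo the rule?** Section 6.5 forbids destroying study records without the sponsor's authorisation, so records may survive outside the database, but it returns nobody to a denominator or to the AE/SAE table. Section 4.9 promises a full SAP, which could define denominators, but it need only be agreed before final data extraction, which may come after removal. Sections 4.9 and 6.7 do not say that removed participants are still counted.

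**The case against.** The strongest reply is that recruitment counts may sit outside the database. Section 4.9 reports the number invited, which includes people who never consented, so some log must exist apart from participants' study data; section 6.7 also lists recruitment data separately from clinic data and questionnaires. On that reading deletion touches only clinical and questionnaire data. Further, if completion were expressed per person invited and the invitation count were kept, removing a non-completer would change nothing.

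This reading is possible, and it makes the completion effect conditional on how the database and the denominator are understood. It does not rescue the AE/SAE table or the reasons for withdrawal, which no text places in such a log.

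The trigger is also narrow: a health or diagnosis change judged to end eligibility, around a four-session course. That stands. A participant with an adverse event who still meets the criteria stays in, drop-outs without a change in health or diagnosis are not clearly covered, and the 2% and 5% rates are illustrations, not evidence. The before and after intervals overlap widely.

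Lastly, section 5.10 also covers a changed diagnosis, and it is fair to ask whether questionnaire scores from someone found not to have severe asthma belong in the main summary. That is a question about one analysis, to be settled openly in the SAP; it is no reason to delete the data.

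**Conclusion.** The concern holds and should be fixed. Section 5.10 states a deletion rule for both phases, and no text exempts completion, attrition, withdrawal reasons or AE/SAE data. Followed as written, it can drop people because they became too unwell to take part.

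Where completion is counted among enrolled participants, one removed non-completer adds 7.1 to 8.3 points when that person is the only non-completer; one removed completer takes off 0.5 to 0.8 points. A sole SAE can disappear from the table.

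These sizes rest on assumed numbers removed and on the database including attendance and safety data. If nobody loses eligibility, nothing changes. The absence of a threshold or test limits the harm to possibly biased description, but completion, attrition and safety are among the results the study is run to report.

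**What to change.** Replace the deletion sentence in section 5.10 with text such as:

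> Where a participant ceases to meet the eligibility criteria after enrolment, all data collected up to that point (attendance, questionnaires, reason for withdrawal, AEs and SAEs) are retained and analysed. All enrolled participants stay in the denominators for attendance, completion, questionnaire return and safety. The number losing eligibility is reported with reasons. Data are removed only where the participant withdraws consent for their use.

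Two passages should be brought into line with this. State whether the optional one-to-one interview is still offered to these participants, so that section 5.10 agrees with sections 4.2 and 4.10. Align section 5.10 with the record-retention text in section 6.5. If questionnaire scores from participants with a changed diagnosis are to be handled separately, for example by showing summaries with and without them, the SAP should say so.

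The cost is one paragraph. The leaflet and consent form are not in the copy reviewed and may need matching wording. Reported completion may come out slightly less favourable. The change concerns data handling only; whether such a participant continues the course is not addressed.
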